2.8 Safety analyses

The safety set will be used for all safety analyses with the exception of the DLT analyses that will use the DDS.

The overall observation period will be divided into three mutually exclusive segments:

- Pre-treatment period: from day of patient's informed consent to the day before first dose of study drug
- On-treatment period:
 - For discontinued patients, from day of first dose of study drug to 30 days after last dose of study drug
 - For ongoing patients, from day of first dose of study drug to the data cut-off date
- Post-treatment period: starting at day 31 days after last dose of study drug

The safety summary tables will include only assessments collected no later than 30 days after study drug discontinuation and assessments prior to the data cut-off date for on-going patients, unless otherwise specified.

For select items, shift tables or change from baseline summaries generated for laboratory, ECG, vital signs and change score (including Karnofsky/Lansky) generation may use data from pre-treatment period for baseline calculations.

All data, regardless of observation period, will be listed and visits/cycles collected in the pre-treatment or post-treatment period will be displayed in all the listings.

2.8.1 Adverse events (AEs)

AEs will be coded using the latest version of MedDRA available prior to clinical database lock and will be graded using Common Terminology Criteria for Adverse Events (CTCAE) version 4.03. If CTCAE grading criteria exists for an AE, grades 1, 2, 3, or 4 corresponding to the severity of mild, moderate, severe, and life threatening, respectively, will be used. CTCAE grade 5 (death) will not be used in this study; rather, this information will be collected on the "End of Treatment" or "Study evaluation completion" eCRF pages.

All AE summaries will be summarized (frequency counts and percentages) by system organ class and/or preferred term, and maximum severity grades, except where otherwise noted. A patient with multiple CTC grades for an AE will be summarized under the maximum CTC grade recorded for the event.

The following AE summaries will be produced:

- AEs regardless of study drug relationship
- AEs suspected to be study drug related
- All deaths, by primary SOC and PT
- On-treatment deaths, by primary system organ class and preferred term
- SAEs regardless of study drug relationship
- SAEs suspected to be study drug related
- AEs associated with study drug discontinuation
- AEs requiring dose adjustment or interruption
- AEs requiring significant additional therapy
- AEs excluding SAEs
- In addition, AEs regardless of study drug relationship will be summarized by PT and age group for MTD/RDE patients.

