The occurrence of adverse events should be sought by non-directive questioning of the patient/guardian during the screening process after informed consent and at each visit during the study. Adverse events also may be detected when they are volunteered by the patient during the screening process or between visits, or through physical examination, laboratory test, or other assessments. As far as possible, each adverse event should be evaluated to determine:

1. The severity grade (CTCAE Grade 1-4).
2. Its duration (Start and end dates) or Ongoing at End of Study.
3. Its relationship to LDK378 (Reasonable possibility that AE is related: No, Yes).
4. Action taken with respect to study or investigational treatment (none, dose adjusted, temporarily interrupted, permanently discontinued, unknown, not applicable).
5. Whether medication or therapy was given (no concomitant medication/non-drug therapy, concomitant medication/non-drug therapy).
6. Whether it is serious, where a serious adverse event (SAE) is defined as in [Section 8.2.1](#).

If the event worsens the event should be reported a second time in the CRF noting the start date when the event worsens in toxicity. For grade 3 and 4 adverse events only, if improvement to a lower grade is determined a new entry for this event should be reported in the CRF noting the start date when the event improved from having been Grade 3 or Grade 4.

Any AE that constitutes a DLT should be reported like a grade 3 and 4 adverse event.

All adverse events should be treated appropriately. If a concomitant therapy is given, this action should be recorded on the Adverse Event eCRF.

Once an adverse event is detected, it should be followed until its resolution or until it is judged to be permanent, and assessment should be made at each visit (or more frequently, if necessary) of any changes in severity, the suspected relationship to LDK378, the interventions required to treat it, and the outcome.

Progression of malignancy (including fatal outcomes), if documented by use of appropriate method (for example, as per RECIST 1.1 criteria for solid tumors or as per IWG guidelines for hematological malignancies), should not be reported as a serious adverse event.

Adverse events separate from the progression of malignancy (example, deep vein thrombosis at the time of progression or hemoptysis concurrent with finding of disease progression) will

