#### 10.7.1.2 Adverse events (AEs)

All AEs recorded during the study will be summarized. The incidence of treatment-emergent AEs (new or worsening from baseline) will be summarized by primary system organ class, severity based on CTCAE version 4.03, type of adverse event, and relationship to LDK378, by treatment group. Deaths reportable as SAEs and non-fatal SAEs will be listed by patient and tabulated by primary system organ class, type of adverse event, and treatment group.

Any other information collected (e.g. start/end dates and duration of adverse event, severity or relatedness to study medication) will be listed as appropriate.

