The safety summary tables will include only assessments collected during the on-treatment period unless otherwise specified. For select items, shift tables or change from baseline summaries generated for laboratory, ECG, and vital signs may use data from pre-treatment period for baseline calculations. See [Section 2.1.1](#) for key definitions of terms used in this SAP.

All data, regardless of observation period, will be listed and assessments collected in the pre-treatment or post-treatment period will be flagged in all the listings.

Subgroup analyses

If the number of patients allows (larger than or equal to 10), in addition to the population subgroups described above, efficacy endpoints (ORR) and adverse events (AEs) will also be summarized for patients in the LDK378 MTD/RDE group by the following subgroups:

- age (1 year to <7 years, 7 years to <12 years, 12 years to <18 years)

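### SAP 2.8.1 omits, without declaring it, the protocol's new-or-worsening condition for AEs, so a grade 3-4 event that starts in screening and improves on drug would count as an on-treatment AE

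*SAP*

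**What the plan says.** **Protocol.** Section 10.7.1.2 makes two statements. The first is general: "All AEs recorded during the study will be summarized". The second sets the incidence analysis: "The incidence of treatment-emergent AEs (new or worsening from baseline) will be summarized by primary system organ class".

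Section 8.1.1 governs how events become records. For worsening: "If the event worsens the event should be reported a second time in the CRF noting the start date when the event worsens". For improvement, a rule that covers grade 3 and 4 events alone: "if improvement to a lower grade is determined a new entry for this event should be reported in the CRF noting the start date" of the improvement. DLTs are to be reported in the same way as grade 3-4 events. AEs are entered on the AE page if they begin or worsen after consent; conditions already present at consent go to medical history. Seriousness and relationship to drug are each assessed per AE.

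**SAP.** Section 2.1: "The safety summary tables will include only assessments collected during the on-treatment period unless otherwise specified". Section 2.8 defines that period as first dose to 30 days after last dose, or to the data cut-off for ongoing patients. Section 2.8.1: "All AE summaries will be summarized (frequency counts and percentages) by system organ class and/or preferred term, and maximum severity grades". It adds that a patient with several grades for an AE is shown under the highest, and it lists a table of "AEs excluding SAEs" among the outputs. Neither section mentions treatment-emergence or a comparison with the grade before first dose. Table 4-1, the list of departures from the protocol, has two entries, both on best overall response. SAP 2.1 does say in general terms that analysis follows section 10 of the protocol.

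**The concern.** The protocol's condition compares an event with its own state before treatment. The SAP's filter looks only at when a record falls. The two agree as long as a new record means the event is new or worse. The CRF breaks that link by also opening a record when a severe event gets better.

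A child whose grade 3 event arose in screening and eased after starting the drug would then appear in the AE tables as having had an on-treatment event. Under the protocol's definition that child contributes nothing. Safety and tolerability is the first secondary objective, and a programmer working from SAP 2.8.1 has no instruction to exclude such records.

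A second question arises from the same CRF rule: whether the lower-grade continuation of an SAE could fall into the table of "AEs excluding SAEs".

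**Working it through.** The plan states no number on this point, so the check compares rules on example records and then bounds the number of patients exposed. The records are invented for illustration; they are not trial data.

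**How records are dated.** The SAP does not say outright that an AE record is placed by its start date. It uses event start date at the data cut-off (SAP 5.1) and imputes partial AE start dates relative to treatment start so that events can be placed in time (SAP 5.6.1). I take start date as the intended rule.

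**Example records**

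| Records | SAP period filter | Protocol condition |
|---|---|---|
| A: grade 3 on day -10, improves to grade 2 on day 6 | 1 AE, grade 2 | 0 |
| A': grade 2 on day -10, worsens to grade 3 on day 6 | 1 AE, grade 3 | 1 AE, grade 3 |
| A'': grade 2 on day -10, improves to grade 1 on day 6 | 0 (no new entry required) | 0 |

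Day -10 lies inside the screening window of day -28 to -1 (protocol Table 7-1). Only pattern A goes wrong. The maximum-grade rule does not repair it: if only on-treatment records are used, the result is a spurious grade 2 AE; if all records of the event are used, it is a spurious on-treatment grade 3 AE. A DLT occurs by definition in the first 21 days of treatment, so its first record is always on-treatment and pattern A cannot arise from it.

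**Patients exposed to pattern A**

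- Total enrolled and treated: 83 (protocol, Amendment 8 rationale).
- Enrolled by 22 September 2016: 40 in escalation + 20 in expansion = 60 (Amendment 6).
- The Amendment 6 log says section 8.1.1 was revised to capture downgrading AEs. If the rule applied from then on, patients whose screening followed it number about 83 - 60 = 23.
- Assumed share with a grade 3-4 AE starting after consent and before first dose, then improving on drug: 2-10%. The documents give no such rate.
- 23 x 0.02 = 0.5 and 23 x 0.10 = 2.3, so roughly 0 to 2 patients.
- If instead the log recorded what sites already did, all 83 are exposed: 83 x 0.02 = 1.7 and 83 x 0.10 = 8.3.

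**The SAE tail.** Patient B has a grade 3 SAE on day 20 that improves to grade 1 on day 24.

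| Serious flag on the day-24 entry | All AEs | SAEs | Non-serious AE table |
|---|---|---|---|
| Kept | 1 | 1 | 0 |
| Not kept | 1 | 1 | 1 |

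Only the last column changes. Even there, the count for a term rises only if the patient has no other non-serious record of that term.

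**The case against.** **The condition has not been removed.** SAP 2.1 defers to protocol section 10, which contains it, and protocol 10.7.1.2 also calls for all recorded AEs to be summarized, so tables without the condition are partly protocol-specified. This stands to the extent that the omission is undeclared and unimplemented, not an explicit deletion. It does not answer the point: the protocol also specifies treatment-emergent incidence, and a general cross-reference gives a programmer no baseline comparison to code.

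**The effect is small.** This stands. Children with progressed malignancy will usually have their symptoms at consent, and those go to medical history. Only a grade 3-4 event arising or worsening in the short gap before first dose can qualify. It would reach the tables regardless of relationship; the drug-related table depends on a separate per-event judgement.

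**A reader might infer that SAEs are routinely counted again as non-serious AEs.** The documents do not support that. They describe the new entry as one for the same event, and they define seriousness separately from grade, so a lower grade is no reason in itself to clear the flag. They do not state whether it is kept.

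**A reader might also infer a broad overstatement of toxicity across all 83 patients.** That needs rates the documents do not give, and it assumes the improvement rule ran from the start. Within any one table, entries for the same patient and term collapse to one.

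**Conclusion.** The point holds in a limited form. As written, SAP 2.8.1 selects AE records by period where the protocol requires new or worsened events. Together with the CRF improvement rule, this gives a wrong count for one defined pattern: a grade 3-4 AE that starts between consent and first dose and improves after it.

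The likely size is 0 to 2 patients. This rests on two assumptions: that the rule took effect with Amendment 6, and that 2-10% of exposed patients show the pattern. Placement by start date is an inference from SAP 5.1 and 5.6.1.

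The SAE tail is conditional. It affects only per-term counts in the table of "AEs excluding SAEs", and only if downgraded entries lose the serious flag. All-AE incidence and SAE incidence are unaffected by it. Neither mechanism touches the DLT analysis, the MTD/RDE or efficacy.

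**What to change.** In SAP 2.8.1:

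1. Restate the protocol definition: count an AE only if it is new on or after first dose, or if its grade exceeds the grade of the same event before first dose.
2. State that an entry recording only an improvement continues its parent event and is not a new AE.
3. Have such entries carry the parent's serious flag when the table of "AEs excluding SAEs" is built.

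If the sponsor prefers the period-only filter, declare it in Table 4-1 with a reason.

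The cost is a few sentences and a small programming step. The documents show no identifier that ties a downgraded entry to its parent, so entries would be matched by patient, term and consecutive dates; ambiguous matches would need a manual check.

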2.8.1.1 Adverse events of special interest

Adverse events of special interest (AESIs) are defined as AEs within the following categories/groupings of preferred terms:

- Hepatotoxicity
- Interstitial lung disease/Pneumonitis
- QT prolongation
- Hyperglycemia
- Bradycardia
- GI toxicity (nausea, diarrhea, vomiting)
- Pancreatitis (including Lipase or amylase increases)

AESIs are defined at the project level and may be updated based on emergent data to reflect new AESIs of interest at the time of analysis. The AESIs listed above will be identified based on a list of preferred terms. The list of preferred terms will be finalized in a separate document.

Frequency counts and percentages of patients with DLTs will be tabulated by treatment group based on the DDS. DLTs will be listed by treatment group and patient.

2.8.2 Laboratory data

The summaries will include all laboratory assessments collected no later than 30 days after last dose of study drug. All laboratory assessments will be listed and those collected later than 30 days after study drug discontinuation will be flagged in the listings. For laboratory data assessments, data from all sources (central and local laboratories) will be combined.

Laboratory data will be classified (by Novartis Oncology CDRR) into CTC grades according to the National Cancer Institute (NCI) CTCAE v4.03. For all reports, CTC grade is always obtained on the converted measurement in SI unit. Grade 5 will not be used. The CTC grade 0 will be assigned as below in different scenarios:

1. For lab parameters defined by criteria based on normal range only, a severity grade of 0 will be assigned when the value is within normal limits.
2. For lab parameters whose grade is defined by criteria based on normal range and absolute values (e.g. platelet count decrease). A severity grade of 0 will be assigned when the value is within normal limits.
3. For lab parameters whose grade is defined by criteria based on normal range and the change from baseline value, with no other associated clinical criteria such as concomitant medication (e.g. creatinine increased) the following will be applied. For the baseline grading and for the grading of post-baseline laboratory values with missing baseline grading, the grade will be derived using the criteria based only on the normal range as per CTCAE v4.03. A severity grade of 0 will be assigned when the post-baseline value is \leq ULN (for hyper) or \geq LLN (for hypo).

Parameters for which a grading does not exist will be classified into low/normal/high group by means of laboratory normal ranges.

The following summaries will be produced for laboratory data (by laboratory parameter):

- Shift tables using CTC grades to compare baseline to the worst post-baseline value for laboratory parameters with CTC grades.
- Shift tables using low, normal, high (as well as low and high combined) classifications to compare baseline to the worst post-baseline value for laboratory parameters where CTC grades are not defined.

Liver function tests (LFTs) of interest for LDK378 are total bilirubin (TBILI), ALT, AST and ALP. In what follows, AT refers to ALT or AST values. LFTs will be summarized as follows:

- Shift tables of baseline vs. worst post-baseline on-treatment values for the categories:
 - TBILI \leq 2xULN, TBILI $>$ 2xULN and missing TBILI
 - ALT \leq 3xULN, ALT $>$ 3xULN and missing ALT
 - AST \leq 3xULN, AST $>$ 3xULN and missing AST
 - ALP $<$ 2xULN, ALP \geq 2xULN and missing ALP
- Frequency counts and percentages of patients with worst post-baseline on-treatment values in the categories:
 - ALT $>$ 3xULN, ALT $>$ 5xULN, ALT $>$ 10xULN, ALT $>$ 20xULN
 - AST $>$ 3xULN, AST $>$ 5xULN, AST $>$ 10xULN, AST $>$ 20xULN
 - AT $>$ 3xULN, AT $>$ 5xULN, AT $>$ 10xULN, AT $>$ 20xULN
 - TBILI $>$ 2xULN

- Concurrent ALT > 3xULN and TBILI > 2xULN
- Concurrent AST > 3xULN and TBILI > 2xULN
- Concurrent AT > 3xULN and TBILI > 2xULN
- Concurrent AT > 3xULN and TBILI > 2xULN and ALP < 2xULN
- Concurrent AT > 3xULN and TBILI > 2xULN and ALP ≥ 2xULN

Concurrent measurements are those occurring on the same date.

In addition, a listing of all TBILI, ALT, AST and ALP values for patients with a post-baseline TBILI > 2xULN, ALT > 3xULN or AST > 3xULN will be provided.

The following listings will be produced by laboratory parameter, treatment group, and patient for all laboratory parameters where CTC grades are defined:

- Listing of patients with laboratory abnormalities of CTC grade 3 or 4
- Listing of all laboratory data with values flagged to show the corresponding CTC grades and the classifications relative to the laboratory reference ranges.

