| Grade 4 (> 10.0 x ULN)  | Permanently discontinue patient from LDK378   |
| AST or ALT   |   |
| Grade 1 (> ULN and ≤ 3.0 x ULN)   | Maintain dose level with LFTs*** monitored per protocol   |
| Grade 2 (> 3.0 and ≤ 5.0 x ULN) without total bilirubin elevation to > 2.0 x ULN  | Maintain dose level with LFTs*** monitored per protocol   |
| Grade 3 (> 5.0 and ≤ 20.0 x ULN) without total bilirubin elevation to > 2.0 x ULN   | Omit dose until resolved to ≤ Grade 1, then ↓ 1 dose level  |
| Grade 4 (> 20.0 x ULN) without total bilirubin elevation to > 2.0 x ULN   | Omit dose until resolved to ≤ Grade 1, then ↓ 1 dose level  |
| AST or ALT and concurrent Total bilirubin  |   |
| AST or ALT > 3.0 x ULN with total bilirubin > 2.0 x ULN in the absence of cholestasis or hemolysis  | Permanently discontinue patient from LDK378. Refer to Section 6.3.2.2 for additional follow-up.                                     |
| AST or ALT > 5.0 and ≤ 20.0 x ULN with total bilirubin > 1.5 and ≤ 3.0 x ULN  | Permanently discontinue patient from LDK378 if event reoccurs after dose reduction.   |
| PANCREATIC   |   |
| Amylase and/or lipase evaluations (in absence of clinical symptoms)   |   |
| Grade 1 (> ULN and ≤ 1.5 x ULN)   | Maintain dose level   |
| Grade 2 (> 1.5 - 2.0 x ULN)   | Maintain dose level   |
| Grade ≥ 3 (> 2.0 x ULN)   | Omit dose until resolved to ≤ Grade 1, then ↓ 1 dose level  |
| Note: Withhold LDK378 for acute onset of new or progressive unexplained abdominal symptoms, such as severe pain or vomiting; perform diagnostic procedures (e.g., abdominal CT scan or ultrasound) to exclude pancreatic pathology. |   |
| RENAL  |   |

| Worst toxicity (CTCAE 4.03 Grade)*               | Dose Modifications for LDK378  |
|---|---|
| Serum creatinine                                 |   |
| Grade 1 (>1 and ≤1.5 x baseline; >ULN and ≤ 1.5 x ULN)  | Maintain dose level   |
| Grade 2 (>1.5 and ≤3.0 x baseline; > 1.5 and ≤ 3 x ULN) | Omit dose until resolved to ≤ Grade 1, then:
If resolved in ≤ 7 days, then maintain dose level
If resolved in > 7 days, then ↓ 1 dose level                         |
| Grade 3 (>3.0 x baseline; > 3.0 and ≤ 6.0 x ULN)        | Omit dose until resolved to ≤ Grade 1, then ↓ 1 dose level  |
| Grade 4 (> 6.0 x ULN)                                   | Permanently discontinue patient from LDK378   |
| GASTROINTESTINAL                                 |   |

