#### 10.7.1.3 Laboratory abnormalities

All laboratory values will be converted into SI units, as appropriate, and the severity grade calculated using CTCAE, version 4.03. Parameters for which a grading does not exist will be classified into low/normal/high group by means of laboratory normal ranges.

For each laboratory test (e.g. hematology, biochemistry etc.) a listing of laboratory values will be provided by laboratory parameter, patient and treatment group. The frequency of notable lab abnormalities (i.e. newly occurring CTCAE grade 3 or 4 laboratory toxicities), will be reported by parameter, cycle and treatment group. Similarly, the frequency of all laboratory abnormalities will be tabulated by parameter, worst CTCAE v4.03 grade experienced, and treatment group. Laboratory data will be summarized by presenting grade shift tables for those parameters that can be classified using CTCAE version 4.03. All remaining data will be summarized by presenting shift tables based on normal ranges.

Laboratory data will be also be displayed by presenting summary statistics of raw data and change from baseline values (means, medians, standard deviations, ranges).

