5.5.3 Laboratory Parameters

This section provides further detail on the analysis of laboratory parameters that will be listed and summarized as described in [Section 2.8.3](#).

Hematology

Hematologic tests include Hemoglobin, platelets, white blood cells (WBC) with differentials (basophils, eosinophils, lymphocytes, monocytes, neutrophils (% or absolute))

The following rules will be applied to derive the WBC differential counts when only percentages are available (this is mainly for neutrophils and lymphocytes, because CTC grading is based on the absolute counts).

The method to convert the value is straightforward: for each subject, the original lab value (%) is divided by 100 and multiplied by WBC count e.g. for neutrophils (NEU):

$$\text{NEU count} = (\text{WBC count}) * (\text{NEU\%value}/100)$$

In order to derive the corresponding absolute normal range, the rule to be applied depends on the availability of the % range and the absolute range for the differential:

- If % absolute range NOT missing (% range is or isn't missing), then use the absolute range provided by the site
- If % range NOT missing and absolute range missing, then the % normal limits (i.e. LLN and ULN) are divided by 100 and multiplied by the corresponding normal limits of WBC count, e.g. for neutrophils NEU):

$$\text{LLN for NEU count} = (\text{LLN for WBC count}) * (\text{LLN for NEU\%value} / 100)$$

$$\text{ULN for NEU count} = (\text{ULN for WBC count}) * (\text{ULN for NEU\%value}/100)$$

Biochemistry

The following calculation will be applied for corrected calcium in SI unit:

Corrected calcium (mmol/L) = measured total Ca (mmol/L) + 0.02 (40 - serum albumin[g/L]), where 40 represents the average albumin level in g/L.

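### The SAP grades any post-baseline creatinine at or below ULN as grade 0 whatever the rise from baseline, so grade 2 or 3 rises within the normal range drop out of the graded laboratory outputs.

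*SAP*

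**What the plan says.** SAP 2.8.2 classifies laboratory data "into CTC grades according to the National Cancer Institute (NCI) CTCAE v4.03", and protocol 10.7.1.3 likewise has "the severity grade calculated using CTCAE, version 4.03". The SAP then sets out in three scenarios how grade 0 is assigned. The third covers parameters graded on both the normal range and the change from baseline, "with no other associated clinical criteria such as concomitant medication (e.g. creatinine increased) the following will be applied".

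Two rules follow. The first is range-only grading "For the baseline grading and for the grading of post-baseline laboratory values with missing baseline grading". The second is "A severity grade of 0 will be assigned when the post-baseline value is" at or below ULN (for parameters where high values are the concern). The second rule does not mention the ratio to baseline.

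Protocol Table 6-4 labels its toxicity column as CTCAE 4.03 grade. For serum creatinine, grade 2 is ">1.5 and ≤3.0 x baseline; > 1.5 and ≤ 3 x ULN", and grade 3 is more than 3.0 times baseline, or above 3.0 and up to 6.0 x ULN. Grade 1 includes any rise above baseline up to 1.5 times.

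SAP section 4 lists two changes to protocol analyses. Both concern best overall response.

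**The concern.** The SAP itself names creatinine as a parameter graded partly on change from baseline, then removes that criterion for every value within range. Patients are children from 12 months of age, and a child who starts well below ULN can double or triple creatinine without crossing it.

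Changes in laboratory values are part of a secondary safety endpoint. The outputs at stake are the table of baseline CTC grade against worst later grade, and the listing of grade 3 or 4 abnormalities. Creatinine is a relevant parameter: protocol Table 1-1 reports an increase in 39 of 255 adults at 750 mg (15.3%), none of them grade 3/4. The output list in SAP 2.8.2 gives liver tests their own threshold tables but gives creatinine none. It also omits the change-from-baseline statistics planned in protocol 10.7.1.3, although SAP 2.1 and 2.8 mention such summaries in passing.

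**Working it through.** **Inputs.** Grade bounds come from protocol Table 6-4 and the in-range rule from SAP 2.8.2, scenario 3. Write *b* for baseline and *v* for the worst post-baseline value, both in multiples of ULN. The documents give no figure to reproduce on this point, and the baselines used below are assumptions.

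**Rules compared.**
- Table 6-4: the worse of the grade from *v/b* and the grade from *v*.
- SAP: grade 0 if *v* ≤ 1; otherwise as Table 6-4, because the SAP does not switch off the baseline criterion above ULN when a baseline exists.
- Proposed: grade 0 if *v* ≤ 1 and *v/b* ≤ 1.5; otherwise as Table 6-4.

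**Where grades can be lost.** A hidden grade 2 needs *v* > 1.5*b* and *v* ≤ 1, so *b* < 1/1.5 = 0.667. A hidden grade 3 needs *v* > 3*b* and *v* ≤ 1, so *b* < 1/3 = 0.333.

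**Examples.**

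| *b* | *v* | *v/b* | Table 6-4 | SAP | Proposed |
|---|---|---|---|---|---|
| 0.50 | 0.80 | 1.60 | 2 | 0 | 2 |
| 0.40 | 0.95 | 2.38 | 2 | 0 | 2 |
| 0.30 | 0.80 | 2.67 | 2 | 0 | 2 |
| 0.25 | 0.80 | 3.20 | 3 | 0 | 3 |
| 0.30 | 1.00 | 3.33 | 3 | 0 | 3 |
| 0.30 | 1.01 | 3.37 | 3 | 3 | 3 |
| 0.40 | 0.60 | 1.50 | 1 | 0 | 0 |
| 0.70 | 1.00 | 1.43 | 1 | 0 | 0 |

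The fifth and sixth rows show a step: from the same baseline, moving from 1.00 to 1.01 x ULN takes the SAP grade from 0 to 3. The last two rows show what the in-range rule may be meant to do, which is to avoid grading small rises.

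**Direction.** Baseline values are graded on the normal range alone, so the in-range rule does not change the baseline grade. It acts only on post-baseline values and can only lower them. For creatinine the shift is therefore understated, never overstated.

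**The case against.** **The grade-0 sentence may apply only when baseline is missing.** It directly follows a sentence limited to baseline values and to missing baseline grading, and could be read as completing it. But the sentence carries no such limit, the three scenarios are introduced as the grade-0 rules, and missing-baseline cases have already been sent to the normal range. If the narrow meaning was intended, the wording still needs correcting.

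**Table 6-4 is a dose-modification table, and its two creatinine criteria are joined only by a semicolon.** If both had to be met, no in-range value would have a grade and there would be no conflict. But a value at 4 times baseline and 2 x ULN would then match no grade: the ratio fits grade 3 and the ULN multiple fits grade 2. Only the either/or reading grades every case.

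**The loss is limited.** This stands. Under protocol 7.2.2.5 and 8.1.1, a laboratory change that requires a change or interruption of study drug must be recorded as an adverse event, and SAP 2.8.1 summarises events requiring dose adjustment or interruption. All raw values are listed. The creatinine DLT criterion in protocol Table 6-2 is above 2 x ULN, which no in-range value can meet. A reader might infer that a child whose drug was held would vanish from the report. The documents do not support that.

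**Neutrophils.** A reader might also infer the same defect in scenario 2, where "a severity grade of 0 will be assigned when the value is within normal limits", because SAP 5.5.3 can derive an absolute limit from percentages "multiplied by the corresponding normal limits of WBC count". The documents do not support this as a finding. It arises only when the absolute range is missing, and protocol 7.2.2.5 requires sites to supply ranges. Whether a grade would be lost depends on local limits that the documents do not give. Scenario 2 also applies to baseline grades, so its effect on a shift could go either way.

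**Conclusion.** The creatinine rule departs from the grading standard that both documents set, and the departure is undeclared. Grade 2 can be lost from any baseline below 0.667 x ULN and grade 3 from any below 0.333 x ULN, provided the worst value stays at or below ULN. The loss is confined to the CTC shift table and, for grade 3, the grade 3/4 listing. In the full listing the raw value remains but the flagged grade would be 0.

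This rests on the plain reading of the grade-0 sentence and on the either/or reading of Table 6-4. The number of children affected cannot be estimated from the documents. The SAP does not say whether ULN is age-specific. If it is, fewer children are likely to start below the two thresholds, but the gap is not removed. The point is worth correcting before reporting; it does not bear on the dose-finding result.

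**What to change.** In SAP 2.8.2, scenario 3:

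- Where a baseline value exists, assign the in-range grade 0 to creatinine only if the value is also no more than 1.5 times baseline. Otherwise assign the worse of the baseline-multiple and ULN-multiple grades.
- Keep range-only grading where the baseline is missing, and say so explicitly.
- Declare in SAP section 4 the convention that remains: in-range rises above 1 and up to 1.5 times baseline, which Table 6-4 calls grade 1, are counted as grade 0.
- Produce the creatinine shift table and the grade 3/4 listing on this basis.

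The cost is a short text change, a section 4 entry and one change to the grading program. No data collection or dosing rule is touched. Creatinine toxicity may look slightly worse, and some small absolute rises from low childhood baselines will receive a grade. Within range the grade will also step from 0 to 2 at 1.5 times baseline, which is the price of leaving grade 1 out.
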